## 8.2 Rationale for study design

The European Medicines Agency (EMA) guideline on strategies to identify and mitigate risks for FIH and early clinical trials with IMPs (EMA/CHMP/SWP/28367/07 Rev. 1) has been considered.

The design of the study is based on the aim to study PK, safety and tolerability of two formulations of GS-248 in a limited number of healthy volunteers. The time points for PK blood sampling have been selected based on data obtained from pre-clinical studies and the FIH study (GS-1001).

A one-sequence design was chosen for the food interaction part of the study to yield a more efficient comparison of treatments than a parallel study design, *i.e.*, fewer subjects might be required since each subject will serve as his own control. To avoid carryover effects, a washout period of at least 4 days has been incorporated between the three treatment administrations. Interim analysis of the FIH study (GS-1001) revealed that none of the subjects receiving multiple doses of 180 mg GS-248 had plasma levels over 5% of  $C_{max}$  at 48 h after the last dose, which indicates that a 4-day wash-out period should be sufficient.

The phototoxicity of GS-248 has not been investigated but based on the MEC value obtained from absorbance studies and the weak and comparatively short-lived potential binding of radioactivity to melanin-containing tissues of the ocular bulb, a phototoxic potential cannot be excluded. Thus, sun protection, as defined in Section 9.6.1, should be used during the study.

GS-248 is a low solubility compound with pH-dependent solubility. A high pH may decrease absorption and thus exposure. For this reason, use of antacids, proton pump inhibitors (PPIs) or any medication that changes gastric pH is not allowed from 14 days prior to IMP administration and until the end-of-study visit.

Overall, the study will provide important data to support the design of further studies, both in healthy volunteers and in patients.

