#### 8.1.1 Part I: Two formulations of GS-248 in fasting conditions

In Part I of the study, a single oral dose of GS-248 in two different solid formulations will be administered to 14 healthy subjects. All subjects will first receive Formulation A (a lipid-based formulation in a capsule) and then Formulation B (a dry powder in a capsule, see Section 10.1). A wash-out period of at least 4 days will be applied between the IMP administrations. Both doses contain 120 mg GS-248. The rationale for the dose is detailed in Section 8.3.

For Part I, subjects will come to the clinic for 4 visits. At Visit 2, subjects will be admitted to the clinic on the afternoon/evening of Day -1 and will remain at the clinic until Day 2 (24 h post dose) for single dose administration of Formulation A and PK and safety assessments. The subjects must fast for at least 10 hours before the anticipated dosing time on Day 1. Water, but no other drinks, is allowed as desired except for 1 h before and 1 h after dosing. The subjects will be carefully monitored by clinical staff during and after dosing. Vital signs and ECG will be checked at regular intervals as detailed in Table 8.1-2. The subjects will return to the clinic on Day 3 (Visit 3) at 48 h post dose for PK blood sampling and safety assessments, as outlined in Table 8.1-1. Safety assessments include AE reporting, physical

examination, ECG, vital signs, body temperature, and blood sampling for analysis of safety laboratory parameters.

Visit 4 will be similar to Visit 2, at which subjects will stay overnight at the clinic from Day -1 to Day 2 for single dose administration of Formulation B and PK blood sampling and safety assessments. Visit 5 will be similar to Visit 3, at which subjects return to the clinic on Day 3 for PK blood sampling and safety assessments.

The schedule of events for Part I is shown in Table 8.1-1 and detailed for visit 2-7 in Table 8.1-2.

Study assessments are described in Section 11.

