## 9.5 Exclusion criteria

Subjects must not enter the study if any of the following exclusion criteria are fulfilled:

1. Known allergy to GS-248.
2. Females who are breast feeding or who plan to become pregnant until 2 weeks after the end-of-study visit.
3. Positive serum or urine pregnancy test (minimum sensitivity 25 IU/L or equivalent units of human chorionic gonadotropin [HCG]) at screening and within 24 h prior to the first administration of IMP.
4. Regular use of corticosteroids (inhaled and systemic), NSAIDs, aspirin or coxibs, antacids, PPIs, or any other medication that changes gastric pH within 14 days of study drug administration.
5. Regular use of any prescribed or non-prescribed medication including analgesics, herbal remedies, vitamins and minerals within 2 weeks prior to the (first) administration of IMP, except hormonal contraception and occasional intake of paracetamol (maximum 2000 mg/day; and not exceeding 3000 mg/week) and nasal decongestants without cortisone, antihistamine or anticholinergics for a maximum of 10 days, at the discretion of the Investigator.
6. Presence of inherited or acquired disorders of platelet function, bleeding or coagulation, as judged by the investigator.
7. History or presence of any clinically significant disease or disorder which, in the opinion of the Investigator, may either put the subject at risk because of participation in the study, or influence the results or the subject's ability to participate in the study.

8. After 10 minutes supine rest at the time of screening, any vital signs values outside the following ranges:
  - Systolic blood pressure <90 or >140 mmHg, or
  - Diastolic blood pressure <50 or >90 mmHg, or
  - Pulse <40 or >90 bpm
9. Positive test for serum hepatitis B surface antigen (HBsAg), hepatitis C virus antibodies (HCVAb) or HIV 1 and/or 2 antibodies at screening.
10. Presence or history of drug and/or alcohol abuse and/or excessive intake of alcohol and/or history, or current use, of anabolic steroids, as judged by the Investigator.
11. Positive test for drugs of abuse or alcohol at screening or on admission to the unit prior to administration of the IMP.
12. Participation in other interventional studies within 3 months prior to administration of study drug.
13. Consumption of grapefruit, grapefruit juice, other grapefruit-containing products, or Seville oranges within 14 days of first IMP administration.

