### 9.6.2 *Prior and concomitant therapy*

#### Prohibited medication

Regular use of corticosteroids (inhaled and systemic), NSAIDs, aspirin, coxibs, antacids, PPIs or any other medication that changes gastric pH is prohibited from 14 days prior to first IMP administration until the end-of-study visit.

Use of corticosteroids (inhaled and systemic), NSAIDs, aspirin, coxibs, antacids, PPIs or any other medication that changes gastric pH, any other prescribed or non-prescribed medication, herbal remedies, vitamin supplements and minerals is prohibited from the first IMP administration until the end-of study visit, except as detailed below.

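### Section 8.2 bars any gastric-pH-changing drug from 14 days before dosing, but the eligibility and medication rules bar only regular use before the first dose, which leaves Formulation A the most exposed period

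*Protocol*

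**What the plan says.** Section 8.2 of the protocol gives the reason for the restriction: GS-248 has low, pH-dependent solubility, and "A high pH may decrease absorption and thus exposure". It concludes that "use of antacids, proton pump inhibitors (PPIs) or any medication that changes gastric pH is not allowed from 14 days prior to IMP administration" and keeps the ban in place until the end-of-study visit. The ban is not limited to regular use.

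The passages that a site applies read differently:

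- Exclusion criterion 4 in 9.5 covers "Regular use of corticosteroids (inhaled and systemic), NSAIDs, aspirin or coxibs, antacids, PPIs, or any other medication that changes gastric pH within 14 days", counted back from dosing. The eligibility list in the synopsis repeats it.
- The first paragraph of 9.6.2 (Prohibited medication) also opens with regular use. That use "is prohibited from 14 days prior to first IMP administration until the end-of-study visit".
- The second paragraph of 9.6.2 drops the word regular, but its ban "is prohibited from the first IMP administration until the end-of study visit, except as detailed below". The allowed-medication text that follows lets the Investigator give other necessary medication during the residential period and does not exclude pH-changing drugs from that permission.

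On order of treatment, section 8.1.1 says: "All subjects will first receive Formulation A (a lipid-based formulation in a capsule) and then Formulation B". The text sets a minimum wash-out of 4 days between doses. Table 8.1-1 shows more than 14 days between Formulation B and the fed dose.

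**The concern.** A site that follows 9.5 and 9.6.2 could dose a volunteer who took an occasional antacid or PPI shortly before the first dose, which is what 8.2 says must not happen. The two paragraphs of 9.6.2 use different words for different windows, so the word regular is hard to dismiss as loose drafting.

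The gap matters because it does not fall equally on the treatments. Every subject takes Formulation A first, so the looser rule falls mainly on A. By the reasoning of 8.2, the expected result is lower exposure after A. That would lower the A/B ratio, which is a primary endpoint, and could influence the PK-based choice of the Part II formulation (section 8.4). If A is chosen, its fasting profile becomes the reference for the food comparison and the fed/fasting ratio would rise.

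The analysis has no clear safeguard. Both PK analysis sets drop subjects for protocol deviations judged to affect the analysis (protocol 17.3.2 and 17.3.3; SAP 5.2.2 and 5.2.3), but use that 9.5 and 9.6.2 permit is not clearly a deviation. SAP 8.1.1.1 has profile-level rules for pre-dose concentrations, emesis, dosing errors and missed samples, and none for pH-changing drugs. SAP 8.2 plans no sensitivity analysis.

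**Working it through.** The plan has no figure of its own to reproduce here. The protocol states that no formal sample size calculation was done, and neither document gives a frequency of antacid or PPI use or a size for the pH effect. Two checks are possible.

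**1. How much of each 14-day look-back falls under the regular-use rule only**

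Inputs: the 14-day window (8.2, exclusion criterion 4, 9.6.2); any use barred from the first dose (9.6.2, second paragraph); minimum gap of 4 days (8.1.1); gap of more than 14 days before the fed dose (Table 8.1-1).

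Formula: exposed days = max(0, 14 - days since the first dose).

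| Dose | Days since first dose | Exposed days of 14 |
|---|---|---|
| Formulation A | 0 | 14 |
| Formulation B, 4-day gap | 4 | 10 |
| Formulation B, 7-day gap | 7 | 7 |
| Formulation B, 14-day gap | 14 | 0 |
| Fed dose, 4 + 14 days (Table 8.1-1) | 18 | 0 |
| Fed dose, 4 + 4 days (text minimum) | 8 | 6 |

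A is the only dose for which occasional use right up to dosing is not barred. For B, any such use lies at least 4 days before dosing.

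**2. Illustrative shift in the A/B ratio**

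Assumptions, not taken from the documents: k of n subjects lose a fraction r of their Formulation A exposure, and B is unaffected. On the log scale the mean difference moves by (k/n) × ln(1 - r), so the ratio is multiplied by (1 - r)^(k/n). The protocol asks for at least 12 evaluable subjects and the SAP reports 14 dosed.

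| k of n | r = 25% | r = 50% | r = 75% |
|---|---|---|---|
| 1 of 12 | -2.4% | -5.6% | -10.9% |
| 2 of 12 | -4.7% | -10.9% | -20.6% |
| 1 of 14 | -2.0% | -4.8% | -9.4% |

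Example: 0.50^(1/12) = 0.944, a shift of -5.6%.

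If the same subject's Formulation B exposure is also cut, the shift shrinks. With A cut by 50% and B by 25%, (0.50/0.75)^(1/12) = 0.967, or -3.3%. With equal cuts it is zero.

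If A is selected for Part II and only its fasting profile is affected, fed/fasting moves by the reciprocal. For 1 of 12 this is 1/0.976 = 1.024 (+2.4%), 1/0.944 = 1.059 (+5.9%) and 1/0.891 = 1.122 (+12.2%) for the three values of r.

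**The case against.** A reader might infer that only the Formulation A period is open to this problem and that the error can only run one way. The documents support neither reading. At the 4-day minimum gap, up to 10 of the 14 days before Formulation B also precede the first dose. The Investigator-discretion exception applies to every residential stay. Section 8.2 says only that a high pH may reduce absorption; it gives no duration of effect and no evidence that the lipid-based and dry-powder capsules respond alike. Use before the first dose could also lower B, which would move A/B the other way.

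There are partial safeguards. Section 11.2.6 collects two weeks of prior medication by interview. Subjects are admitted the afternoon or evening before dosing and fast for at least 10 hours. Section 8.2 is itself protocol text, so use contrary to it could be argued to be a deviation. Exclusion criterion 5 makes an exception for occasional paracetamol, which may imply that other occasional use is not accepted.

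These arguments limit the size of the problem but do not remove the contradiction. The main clause of exclusion criterion 5 again says "Regular use of any prescribed or non-prescribed medication including analgesics, herbal remedies, vitamins and minerals within 2 weeks prior to the (first) administration of IMP", so the implied ban is an inference. Whether permitted occasional use counts as a deviation is exactly what the conflicting passages leave unsettled.

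It is also fair to say that confounding of period with formulation belongs to any one-sequence design and is not created by this wording. It does mean that the model cannot correct the comparison afterwards, so affected profiles have to be found from the medication records.

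**Conclusion.** The point holds: wrong as written, because the rule that sites apply is weaker than the safeguard stated in 8.2. Formulation A is the most exposed period, Formulation B is partly exposed, and the fed dose is not exposed if the gap in Table 8.1-1 is kept. The expected direction is a lower A/B ratio and, if A is selected, a higher fed/fasting ratio.

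The size is unknown. The range of -2.4% to -10.9% assumes 1 of 12 subjects affected, a 25% to 75% loss and an effect confined to A. It is smaller with 14 subjects or if B is affected too, and larger if more subjects are affected. It shows only that in a sample this small, one affected subject can move a primary ratio noticeably. This point should be corrected, but it does not by itself invalidate the comparison.

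**What to change.** Reconcile protocol section 8.2, exclusion criterion 4, its synopsis copy and section 9.6.2 so that one rule on pH-changing drugs applies identically before all three doses. Taking these drugs out of the shared sentence on regular use would make that straightforward. Which rule is right is a matter for the sponsor and the investigator.

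In SAP 8.1.1.1, add that any profile with a recorded pH-changing drug in the 14 days before that dose will be identified from the prior and concomitant medication data and individually assessed for its effect on the PK comparison. The SAP already does this for pre-dose concentrations above 5% of Cmax and for missed samples. The line does not presume that such use is a deviation, so it works under either protocol rule. It needs no new data and still helps if dosing is complete, as the SAP's past tense about the 14 subjects suggests.

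Cost: wording changes in four places in the protocol and one line in the SAP. If the 8.2 wording is the one kept, possibly a few more screen failures or re-screenings.

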## 8.3 Selection of dose

A dose of 120 mg is selected to mimic the planned phase IIa study. Provisional data from the FIH phase I study (GS-1001) suggest that a dose of 120 mg is safe and tolerable.

## 8.4 Selection of formulation

After completion of Part I, PK data will be evaluated to determine which of the two formulations is to be used in Part II, the food interaction part. The selection will be based on PK parameters, *e.g.*, projected AUC and plasma level at the end of dosing intervals in repeated dose scenarios.

## **9 STUDY POPULATION**

Prospective approval of protocol deviations to eligibility criteria, also known as protocol waivers or exemptions, is not permitted.

### **9.1 Recruitment**

The subjects will be recruited from CTC's database of healthy volunteers and from advertising in media (including social media).

### **9.2 Screening and enrolment log**

Investigators must keep a record of all screened subjects even if they were not subsequently included in the study. This information is necessary to verify that subjects were selected without bias. The reason for screen failure should be stated for all subjects screened but not included. The reason for withdrawal should be stated for all subjects included but not completed.

A screening number will be allocated to each subject in connection to the informed consent process at the Screening visit. The screening number is generated automatically in the electronic case report form (eCRF). The screening number will allow identification of subjects irrespective of their possible eligibility for the study.

If a subject cannot receive the planned dose of IMP within four weeks after screening (*i.e.*, the time interval between signing informed consent until dose administration) the subject should be rescreened and assigned a new screening number before proceeding in the study.

### **9.3 Number of subjects**

Approximately 20 healthy subjects will be screened to achieve a total of 14 dosed subjects, and at least 12 evaluable subjects. In the event of early withdrawals, subjects may be replaced.

### **9.4 Inclusion criteria**

For inclusion in the study, subjects must fulfil the following criteria:

1. Willing and able to give written informed consent for participation in the study.
2. Healthy male or female subject aged  $\geq 18$  and  $\leq 70$  years.
3. Body Mass Index (BMI)  $\geq 19.0$  and  $\leq 30.0$  kg/m^2.
4. Clinically normal medical history, physical findings, vital signs, ECG and laboratory values at the time of screening, as judged by the Investigator.
5. Women of child bearing potential (WOCBP) must practice abstinence from heterosexual intercourse (only allowed when this is the preferred and usual lifestyle of the subject) or must agree to use a highly effective method of contraception with a failure rate of  $< 1\%$  to prevent pregnancy (combined [oestrogen and progestogen

containing] hormonal contraception [oral, intravaginal, transdermal], progestogen-only hormonal contraception associated with inhibition of ovulation [oral, injectable, implantable], intrauterine device [IUD] or intrauterine hormone-releasing system [IUS]) from at least 4 weeks prior to dose to 4 weeks after last dose. Female subjects must refrain from donating eggs from the date of dosing until 3 months after dosing with the IMP. Their male partner must agree to use a condom during the same time frame if he has not undergone vasectomy.

Women of non-childbearing potential are defined as pre-menopausal females who are sterilised (tubal ligation or permanent bilateral occlusion of fallopian tubes); or post-menopausal defined as 12 months of amenorrhea (in questionable cases a simultaneous blood sample with simultaneous detection of follicle stimulating hormone [FSH] 25-140 IE/L).

Male subjects must be willing to use condom, be vasectomised or practice abstinence from heterosexual intercourse (only allowed when this is the preferred and usual lifestyle of the subject) to prevent pregnancy and drug exposure of a partner. Male subjects must refrain from donating sperm from the date of dosing until 3 months after dosing with the IMP. Their female partner of child-bearing potential must use contraceptive methods with a failure rate of < 1% to prevent pregnancy (see above).

## 9.5 Exclusion criteria

Subjects must not enter the study if any of the following exclusion criteria are fulfilled:

1. Known allergy to GS-248.
2. Females who are breast feeding or who plan to become pregnant until 2 weeks after the end-of-study visit.
3. Positive serum or urine pregnancy test (minimum sensitivity 25 IU/L or equivalent units of human chorionic gonadotropin [HCG]) at screening and within 24 h prior to the first administration of IMP.
4. Regular use of corticosteroids (inhaled and systemic), NSAIDs, aspirin or coxibs, antacids, PPIs, or any other medication that changes gastric pH within 14 days of study drug administration.
5. Regular use of any prescribed or non-prescribed medication including analgesics, herbal remedies, vitamins and minerals within 2 weeks prior to the (first) administration of IMP, except hormonal contraception and occasional intake of paracetamol (maximum 2000 mg/day; and not exceeding 3000 mg/week) and nasal decongestants without cortisone, antihistamine or anticholinergics for a maximum of 10 days, at the discretion of the Investigator.
6. Presence of inherited or acquired disorders of platelet function, bleeding or coagulation, as judged by the investigator.
7. History or presence of any clinically significant disease or disorder which, in the opinion of the Investigator, may either put the subject at risk because of participation in the study, or influence the results or the subject's ability to participate in the study.

8. After 10 minutes supine rest at the time of screening, any vital signs values outside the following ranges:
  - Systolic blood pressure <90 or >140 mmHg, or
  - Diastolic blood pressure <50 or >90 mmHg, or
  - Pulse <40 or >90 bpm
9. Positive test for serum hepatitis B surface antigen (HBsAg), hepatitis C virus antibodies (HCVAb) or HIV 1 and/or 2 antibodies at screening.
10. Presence or history of drug and/or alcohol abuse and/or excessive intake of alcohol and/or history, or current use, of anabolic steroids, as judged by the Investigator.
11. Positive test for drugs of abuse or alcohol at screening or on admission to the unit prior to administration of the IMP.
12. Participation in other interventional studies within 3 months prior to administration of study drug.
13. Consumption of grapefruit, grapefruit juice, other grapefruit-containing products, or Seville oranges within 14 days of first IMP administration.
14. Any clinically significant illness, medical/surgical procedure or trauma within 4 weeks of the first administration of IMP.
15. Malignancy within the past 5 years with the exception of in situ removal of basal cell carcinoma.
16. Any planned major surgery within the duration of the study.
17. Prolonged QTcF (>450 ms), cardiac arrhythmias or any clinically significant abnormalities in the resting ECG, as judged by the Investigator.
18. Current smokers or users of nicotine products. Irregular use of nicotine (*e.g.*, smoking, snuffing, chewing tobacco) less than three times per week is allowed before screening visit.
19. Regular excessive caffeine consumption defined by a daily intake of >5 cups of caffeine-containing beverages.
20. Intake of xanthine- and/or taurine-containing energy drinks within 2 days prior to screening and prior to IMP administration.
21. Plasma donation within one month of screening or blood donation (or corresponding blood loss) during three months prior to screening.
22. Investigator considers the subject unlikely to comply with study procedures, restrictions and requirements.
23. Estimated glomerular filtration rate (eGFR) < 50 mL/min/1.73 m^2 (determined by the revised Lund-Malmö GFR estimating equation).
24. Subjects with swallowing disorders, which may affect the subject's capability to swallow the IMP.
25. Subjects who are vegetarian or for other reasons cannot eat the high-fat high-calorie breakfast.

